5.2.2. Baseline (First dosing day / Day 0)

- Physical examination and vital signs;
- Body weight;
- 12 leads ECG;
- Hematology and Biochemistry panel;
- Urine Pregnancy (β -HCG) test for all women of childbearing potential;

- Pharmacokinetics blood samples at 1h-, 2h- and 3-hours post-dose;
- Blood samples for acute phase reactants (CRP & ESR);
- Blood (gel tubes and Truculture® tubes) samples for cytokines determination;
- Blood samples (Paxgene® tubes) for miR-124 dosage;
- Blood samples for flow cytometry cells count (including at least B & T lymphocytes, myeloid cells and macrophages) (only in the Coordinating Investigator's site);
- Tender/painful joint count (28) (TJC28);
- Swollen joint count (28) (SJC28);
- Patient global assessment of disease (PtGA);
- Patient assessment of joint pain (Pain-VAS);
- Investigator global assessment of disease (PrGA);
- Disability index of the healthy assessment questionnaire (HAQ-DI);
- Functional Assessment of Chronic Illness Therapy (FACIT)-Fatigue;
- Record any concomitant medications;
- Confirm the wash-out of the anti-TNF α therapy is complete;
- Adverse Events reporting;
- Randomization;
- Dispense study treatment to patient and instruct how to take them (first dosing at site);
- Dispense patient diary (for treatment compliance and adverse event recording) and instruct how to complete them;
- Schedule next patient visits.

5.2.3. Week 1 / Day 7 (+/- 2 days) - Visit 1

- Physical examination and vital signs;
- Body weight;
- Hematology and Biochemistry;
- Blood samples for cytokines determination
- Record any concomitant medications;
- Check treatment compliance on patient diary;
- Adverse Events reporting;
- Schedule next patient visits.

5.2.4. Week 2 / Day 14 (+/- 2 days), Week 4 / Day 28 (+/- 2 days), Week 8 / Day 56 (+/- 2 days), Week 12 / Day 84 (+/- 2 days) - Visits 2, 3, 4, 5

- Physical examination and vital signs;
- Body weight;
- 12-leads ECG (D84 only);
- Hematology and Biochemistry panel;
- Blood pregnancy test for all women of childbearing potential (except on Week 2);
- Pharmacokinetics blood samples pre-dose, 1h-, 2h- and 3-hours post-dose (Week 2 / Day 14 and Week 8 / Day 56 only);
- Blood samples for acute phase reactants (CRP, ESR);
- Blood samples (gel tubes) for cytokines determination;
- Blood samples (Truculture® tubes) for cytokines determination at Week 8 only;
- Blood samples (Paxgene® tubes) for miR-124 qPCR dosage (Week 8 only);

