3.3 STUDY TREATMENT

Medications:

- ABX464 or its matching placebo administered once daily;
- MTX \geq 10 mg/week, at stable dose, throughout the study; the maximal dose of methotrexate should not exceed a total of 20 mg/week;
- Folic acid \geq 5 mg/week post MTX dose, to minimize MTX toxicity.

A total of 60 patients will be recruited sequentially to receive the following doses:

	Intervention/treatment Active Arm
Group #1 (n=20): 100mg qd	2 capsules of 50mg ABX464
Group #2 (n=20): 50mg qd	1 capsule of 50mg ABX464 + 1 capsule of matching placebo
Group #3 (n=20): Placebo	2 capsules of matching Placebo

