5 DEFINITIONS AND DERIVED VARIABLES

5.1 DEFINITIONS

Study Drug: Study drug is taken to mean either ABX464 or placebo.

Baseline: Baseline is defined by patient and by variable as the last non-missing value before the first dose of study drug

Study Day: Study day is the number of days since start of treatment where the date of first dose is counted as Day 0.

Treatment Exposure: Treatment exposure is the number of days during the treatment period that the patient was exposed to the study treatment and is calculated as:

$$(\text{Date_of_last_dose}) - (\text{Date_of_first_dose}) + 1$$

Compliance: Compliance is the number of doses actually taken divided by the scheduled number of doses expressed as a percentage.

Non-compliance: Non-compliance is defined as taking less than 80% or more than 120% of study medication.

Protocol Deviation: a deviation related to study inclusion or exclusion criteria, conduct of the trial, patient management or patient assessment. This refers to any change, divergence, or departure from the study design or procedures defined in the protocol. Deviations recorded by the Project Manager or CRA, or detected by Data Management or by Statistical programming checks as described in Section 6.3 will be identified and discussed at the Data Review Meeting before database lock to agree which should be included in Listing I6.2.2.

Screening and enrollment: Screening is the process of active evaluation of potential participants for enrollment in a trial. After a patient is recruited, screening occurs during the enrollment period to see if they meet the inclusion and exclusion criteria. If they meet the criteria, the subject is eligible to enroll in the trial.

Baseline and Screening failure: A patient is considered to be a baseline failure if the patient signs the informed consent but withdraws before the screening visit. A patient who does not fulfil the randomization criteria will be considered as a screening failure.

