11.8 PRIOR AND CONCOMITANT MEDICATION

All medications taken by patients on entry to the study or during the study will be recorded in the CRF. Medications will be classified using the version of the World Health Organisation Drug Dictionary (WHODD) coding dictionary defined in the Data Management Plan. The Anatomical Therapeutic Chemical (ATC) Classification and WHO-DRUG PT will be used to list and summarise the data.

If required by client, conmeds can be summarised at 3 levels: ATC levels 1 and 2 and preferred term.

Prior medications are defined as medication that started and stopped before Day 1. Only medications where the stop date is prior to Day 1 will be considered prior. If the stop date is unknown or incomplete and the medications cannot definitely be considered as stopped prior to Day 1 then the medications will be considered as concomitant medications at randomisation or change in concomitant medication, depending on the start date.

Concomitant medications at randomisation are defined as medications that started before Day 1 and either stopped on Day 1 or continued into the study. Partial start dates where the medication cannot

definitely be considered as starting prior to Day 1 will lead to a categorisation of the medications as having started on or after dosing.

Change in concomitant medication is defined as medication that started on or after Day 1. If the medication start or stop dates are partial then the rules for prior and concomitant medication, detailed above will be observed prior to assigning a category.

The number (%) of patients reporting the use of any prior medications and the number (%) of patients taking each drug by ATC classification and PT will be summarised using the FAS (Table 14.3.8). This table will be repeated for concomitant medications at randomisation (Table 14.3.9.1) and for change in concomitant medication (Table 14.3.9.2)

Mandatory concomitant treatments are the followings:

- MTX \geq 10 mg/week, at stable dose, throughout the study;
- Folic acid \geq 10 mg/week post MTX dose, to minimize MTX toxicity.

Allowed Concomitant Medications are the followings:

- Corticosteroids at stable dose of prednisone and prednisone equivalent \leq 10 mg/day during the study;
- Non-steroidal anti-inflammatory drugs (NSAIDs) at stable dose during the study;
- Antalgics including class III at stable dose during the study;
- Other non-rheumatologic medications.

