	ABX-464 100mg (N=xx)	ABX-464 50mg (N=xx)	Placebo (N=xx)	Total (N=xx)
Any prior medication ¹	xx (xx.x%)	xx (xx.x%)	xx (xx.x%)	xx (xx.x%)
X, xxxxxxxxxxxxxxxx	xx (xx.x%)	xx (xx.x%)	xx (xx.x%)	xx (xx.x%)
X0N, xxxxxxxxxxxxxxxx	xx (xx.x%)	xx (xx.x%)	xx (xx.x%)	xx (xx.x%)
X0NXX, xxxxxxxxxxxxxxxx	xx (xx.x%)	xx (xx.x%)	xx (xx.x%)	xx (xx.x%)
xxxxxxxxxxxxxxxxxx	xx (xx.x%)	xx (xx.x%)	xx (xx.x%)	xx (xx.x%)
Etc	xx (xx.x%)	xx (xx.x%)	xx (xx.x%)	xx (xx.x%)
X0NXX, xxxxxxxxxxxxxxxx	xx (xx.x%)	xx (xx.x%)	xx (xx.x%)	xx (xx.x%)
xxxxxxxxxxxxxxxxxx	xx (xx.x%)	xx (xx.x%)	xx (xx.x%)	xx (xx.x%)
Etc	xx (xx.x%)	xx (xx.x%)	xx (xx.x%)	xx (xx.x%)
X0N, xxxxxxxxxxxxxxxx	xx (xx.x%)	xx (xx.x%)	xx (xx.x%)	xx (xx.x%)
X0NXX, xxxxxxxxxxxxxxxx	xx (xx.x%)	xx (xx.x%)	xx (xx.x%)	xx (xx.x%)
xxxxxxxxxxxxxxxxxx	xx (xx.x%)	xx (xx.x%)	xx (xx.x%)	xx (xx.x%)
Etc	xx (xx.x%)	xx (xx.x%)	xx (xx.x%)	xx (xx.x%)
Etc				
Etc				

¹ Medication that stopped prior to date of first dose.

WHO-DDE version <XX.X>

The denominator for each percentage is the number of patients in the full analysis set within the column.

Source: Listing 16.4.12.1

Path\Filename

Page x/y

*This layout also applies to:
Table 14.3.9.1 Concomitant Medications (Full Analysis Set)*

ABX464-301

ddMMMyyyy

Table 14.3.9.2 Change in Concomitant Medications (Full Analysis Set)

	ABX-464 100mg (N=xx)	ABX-464 50mg (N=xx)	Placebo (N=xx)	Total (N=xx)
Any concomitant medication	xx (xx.x%)	xx (xx.x%)	xx (xx.x%)	xx (xx.x%)
X, xxxxxxxxxxxxxxxx	xx (xx.x%)	xx (xx.x%)	xx (xx.x%)	xx (xx.x%)
X0N, xxxxxxxxxxxxxxxx	xx (xx.x%)	xx (xx.x%)	xx (xx.x%)	xx (xx.x%)
X0NXX, xxxxxxxxxxxxxxxx	xx (xx.x%)	xx (xx.x%)	xx (xx.x%)	xx (xx.x%)
xxxxxxxxxxxxxxxx	xx (xx.x%)	xx (xx.x%)	xx (xx.x%)	xx (xx.x%)
Etc	xx (xx.x%)	xx (xx.x%)	xx (xx.x%)	xx (xx.x%)
X0NXX, xxxxxxxxxxxxxxxx	xx (xx.x%)	xx (xx.x%)	xx (xx.x%)	xx (xx.x%)
xxxxxxxxxxxxxxxx	xx (xx.x%)	xx (xx.x%)	xx (xx.x%)	xx (xx.x%)
Etc	xx (xx.x%)	xx (xx.x%)	xx (xx.x%)	xx (xx.x%)
X0N, xxxxxxxxxxxxxxxx	xx (xx.x%)	xx (xx.x%)	xx (xx.x%)	xx (xx.x%)
X0NXX, xxxxxxxxxxxxxxxx	xx (xx.x%)	xx (xx.x%)	xx (xx.x%)	xx (xx.x%)
xxxxxxxxxxxxxxxx	xx (xx.x%)	xx (xx.x%)	xx (xx.x%)	xx (xx.x%)
Etc	xx (xx.x%)	xx (xx.x%)	xx (xx.x%)	xx (xx.x%)

Etc

Etc

WHO-DDE version <XX.X>

The denominator for each percentage is the number of patients in the full analysis set within the column.

Source: Listing 16.4.12.3

Path\Filename

ABX464-301

ddMMMyyyy

Listing 16.2.1.1 Patient Disposition

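### SAP 11.8 splits prior from new medication at Day 1 although SAP 5.1 makes the first dose Day 0, so a drug started after dosing on Day 0 never reaches the table of new medication; its folic acid minimum also disagrees with the rest of the plan

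*SAP*

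**What the plan says.** **Day numbering.** SAP 5.1: "Study day is the number of days since start of treatment where the date of first dose is counted as Day 0". Protocol 5.2.2 agrees. Its Baseline / Day 0 visit includes "Dispense study treatment to patient and instruct how to take them (first dosing at site").

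**Medication categories.** SAP 11.8 defines three, each with its own table:

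- Prior (Table 14.3.8): "Prior medications are defined as medication that started and stopped before Day 1".
- At randomisation (Table 14.3.9.1): "Concomitant medications at randomisation are defined as medications that started before Day 1 and either stopped on Day 1 or continued into the study".
- New (Table 14.3.9.2): "Change in concomitant medication is defined as medication that started on or after Day 1".

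For partial start dates, the same section treats a drug that cannot be placed before Day 1 as one begun at or after dosing. The footnote to the Table 14.3.8 shell in SAP 15 defines prior as "Medication that stopped prior to date of first dose".

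**Background treatment.** SAP 11.8 lists mandatory folic acid with a minimum of "10 mg/week post MTX dose, to minimize MTX toxicity". SAP 3.3 has a minimum of "5 mg/week post MTX dose, to minimize MTX toxicity". SAP 3.2.1 and Protocol 4.2.1 and 5.12.1 also state 5 mg/week. The methotrexate line in 11.8 gives the lower limit without the 20 mg/week ceiling that appears in those other sections.

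**The concern.** If the first dose is on Day 0, then everything before Day 1 includes the whole dosing day. A painkiller or antiemetic first taken some hours after the first capsule would be tabulated with treatment that patients brought into the trial. It would be absent from the table meant to show what was added after dosing began.

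Safety is the primary objective, and Protocol 1.2.6 reports headache, nausea and vomiting as the main events, with peak concentration about 2 hours after a dose. Protocol 5.12.2 also asks for NSAIDs and analgesics at stable dose. A new analgesic on the dosing day is therefore something a reader would expect to find in Table 14.3.9.2.

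The rule is also out of step with SAP 11.6.1, which makes an event treatment-emergent from the date and time of first dosing. A headache after the Day 0 dose would be treatment-emergent while the drug given for it could be listed as prior.

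On folic acid, a patient taking at least 5 but less than 10 mg/week meets the requirement in SAP 3.3 and fails the one in SAP 11.8.

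**Working it through.** There is no power or sample size figure to reproduce. The check applies the three definitions in SAP 11.8 to start and stop days. It does so first with the cut at Day 1 as written, and then with the cut at the date of first dose (Day 0, from SAP 5.1).

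Rule, for a cut day *c*: prior if start < *c* and stop < *c*; at randomisation if start < *c* and the drug is not prior; change if start ≥ *c*.

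| Start | Stop | As written (*c* = 1) | Cut at first dose (*c* = 0) |
|---|---|---|---|
| Day −10 | Day −2 | Prior | Prior |
| Day −10 | Day 0 | Prior | At randomisation |
| Day −10 | Day 1 or ongoing | At randomisation | At randomisation |
| Day 0 | Day 0 | Prior | Change |
| Day 0 | Day 1, Day 5 or ongoing | At randomisation | Change |
| Day 1 | Day 1, Day 3 or ongoing | Change | Change |

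1. All four Day 0 start patterns (stop on Day 0, stop on Day 1, stop on Day 5, ongoing) miss Table 14.3.9.2 as written. All four enter it when the cut is the first-dose date.
2. Only one of the four, started and stopped on Day 0, is called prior. The other three go to the at-randomisation table.
3. Starts on Day 1 or later are classed the same way under both cuts.
4. A drug begun before Day 0 and stopped on Day 0 moves between the first two tables. It does not bear on new medication.

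The Table 14.3.8 footnote settles only part of this. Suppose it is followed for the prior table and the 11.8 text for the other two. A drug started and stopped on Day 0 is then not prior, because it did not stop before the date of first dose. It is not a change, because it started before Day 1. It is not clearly at randomisation either, because it neither stopped on Day 1 nor plainly continued. It may appear in no table.

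Size per patient, at the planned 20 per arm: 1/20 = 5 percentage points in any row that the patient enters or leaves.

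Folic acid: 10/5 = 2, a twofold difference in the stated minimum. SAP 1.2, which lists changes from the protocol, mentions only the efficacy sets.

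**The case against.** The best defence is that the intended meaning is evident. The partial-date rule in 11.8 and the Table 14.3.8 footnote both point to the dosing day, so a careful programmer would use it, and SAP 12 requires unique tables to be programmed independently, which could expose the ambiguity. This shows that the slip may be caught. It does not remove the three definitions, each of which says Day 1, and the Table 14.3.9.2 shell carries no rule of its own.

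The defence is right about consequences. The listings keep the information: the medication listings (16.4.12.1 to 16.4.12.3) show dates, indication and any linked adverse event, and the adverse event listing (16.2.7) shows the drug given. A Day 0 antiemetic can be traced whatever its category.

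Several stronger readings are tempting, and the documents do not support them:

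- *That drugs given for first-dose side effects are in general reported as pre-treatment.* This is true only of Day 0 starts, and only those also stopped on Day 0 are called prior.
- *That Day 0 medication is where the arms will differ.* The protocol gives the time of peak concentration and the type of event, but no onset times, and nothing in the plan names Table 14.3.9.2 as the check for imbalance between arms.
- *That folic acid or methotrexate compliance will be misreported.* Compliance in SAP 5.1 and Table 14.3.7 concerns study drug, and no listed table computes it for background treatment.
- *That leaving out the methotrexate ceiling contradicts the protocol.* It is an omission from a restated list, not a different limit.

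**Conclusion.** The point holds in a limited form. As written, SAP 11.8 contradicts SAP 5.1, its own partial-date rule, the Table 14.3.8 footnote and the treatment-emergent rule in SAP 11.6.1. Followed literally, it keeps every medication started after dosing on Day 0 out of Table 14.3.9.2.

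The effect is confined to descriptive medication tables. The primary comparison of treatment-emergent events and the ACR20 comparison do not use them. The number of patients affected cannot be estimated from the documents; the 5 points per patient assumes 20 per arm in the Full Analysis Set. The conclusion also assumes that the programmer follows the 11.8 text rather than the footnote, a choice that the SAP leaves open.

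The folic acid discrepancy is a separate and plain contradiction between sections. Its practical effect depends on whether a deviation check is ever built from 11.8. I take no view on which minimum is right.

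**What to change.** 1. In SAP 11.8, replace Day 1 with the date of first dose (Day 0) in all three definitions and in the partial-date rules. This brings the section into line with SAP 5.1 and the Table 14.3.8 footnote.
2. Add a default: a medication with a Day 0 start counts as new unless its indication, its adverse event link or any recorded time shows that it began before the first dose.
3. Reconcile the folic acid minimum across SAP 11.8, SAP 3.2.1, SAP 3.3 and Protocol 4.2.1 and 5.12.1, and align the methotrexate wording in 11.8 with those sections, before any deviation check uses 11.8.

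The cost is a few words in the SAP before programming is final. There is one small downside. The medication listing shows start dates without times, so under the default some drugs begun on Day 0 before dosing may be counted as new.

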12 VALIDATION

All tables, figures and listings will be subject to independent quality control and visual review. Unique tables will be independently programmed. Findings will be documented in a quality control form and actions taken will also be documented.

The completed form will be reviewed and signed by both programmers and by the head of biostatistics.

13 LITERATURE CITATIONS/REFERENCES

Not applicable

14 LIST OF TABLES, FIGURES AND LISTINGS

14.1 LIST OF TABLES

Demographic Data

Table 14.1.1	Screening Failures	All Enrolled Patients
Table 14.1.2	Patient Disposition	All Randomised Patients
Table 14.1.3	Study Termination and Primary Reason for Withdrawal	All Randomised Patients
Table 14.1.4	Demographic and Baseline Characteristics	Full Analysis Set
Table 14.1.5.1	Medical History	Full Analysis Set
Table 14.1.5.2	Current Medical Conditions	Full Analysis Set

Efficacy Data

Table 14.2.1.1	Analysis of ACR20 Response Rate	Efficacy Set 1
Table 14.2.1.2	Analysis of ACR20 Response Rate	Efficacy Set 2
Table 14.2.1.3	Analysis of ACR20 Response Rate	PP Set
Table 14.2.2.1	Summary of Categorical ACR20 Response at Week 12	Efficacy Set 1
Table 14.2.2.2	Summary of Categorical ACR20 Response at Week 12	Efficacy Set 2
Table 14.2.3.1	Analysis of the individual components of the ACR20 response	Efficacy Set 1
Table 14.2.3.2	Analysis of the individual components of the ACR20 response	Efficacy Set 2
Table 14.2.4.1.1	Analysis of ESR	Efficacy Set 1
Table 14.2.4.1.2	Analysis of ESR	Efficacy Set 2
Table 14.2.4.2.1	Analysis of DAS28-CRP	Efficacy Set 1
Table 14.2.4.2.2	Analysis of DAS28-CRP	Efficacy Set 2
Table 14.2.4.3.1	Analysis of DAS28-ESR	Efficacy Set 1
Table 14.2.4.3.2	Analysis of DAS28-ESR	Efficacy Set 2
Table 14.2.4.4.1	Analysis of SDAI Score	Efficacy Set 1
Table 14.2.4.4.2	Analysis of SDAI Score	Efficacy Set 2
Table 14.2.4.5.1	Analysis of CDAI Score	Efficacy Set 1

Table 14.2.4.5.2	Analysis of CDAI Score	Efficacy Set 2
Table 14.2.4.6.1	Summary of FACIT-Fatigue Score	Efficacy Set 1
Table 14.2.4.6.2	Summary of FACIT-Fatigue Score	Efficacy Set 2
Table 14.2.5.1	Summary of Patients Different Responses and Remissions	Efficacy Set 1
Table 14.2.5.2	Summary of Patients Different Responses and Remissions	Efficacy Set 2

Safety Data

Table 14.3.1.1	Summary of Adverse Events	Safety Set
Table 14.3.1.2.1	Analysis of all Treatment-Emergent Adverse Events	Safety Set
Table 14.3.1.2.2	Treatment-Emergent Adverse Events, by SOC and PT: Period 1	Safety Set
Table 14.3.1.2.3	Treatment-Emergent Adverse Events, by SOC and PT: Period 2	Safety Set
Table 14.3.1.3.1	Serious Treatment-Emergent Adverse Events, by SOC and PT: Period 1	Safety Set
Table 14.3.1.3.2	Serious Treatment-Emergent Adverse Events, by SOC and PT: Period 2	Safety Set
Table 14.3.1.4.1	Treatment-Emergent Adverse Events Leading to Study Drug Discontinuation, by SOC and PT: Period 1	Safety Set
Table 14.3.1.4.2	Treatment-Emergent Adverse Events Leading to Study Drug Discontinuation, by SOC and PT: Period 2	Safety Set
Table 14.3.1.5.1	Treatment-Emergent Adverse Events of Grade 3 or 4 by SOC and PT: Period 1	Safety Set
Table 14.3.1.5.2	Treatment-Emergent Adverse Events of Grade 3 or 4 by SOC and PT: Period 2	Safety Set
Table 14.3.2.1	Listing of Deaths	Safety Set
Table 14.3.2.2	Listing of Serious Adverse Events	Safety Set
Table 14.3.2.3	Listing of Withdrawals Due to Adverse Events	Safety Set
Table 14.3.3.1	Summary of Laboratory Parameters: Haematology	Safety Set
Table 14.3.3.2	Summary of Laboratory Parameters: Biochemistry	Safety Set
Table 14.3.3.3	Listing of Abnormal Laboratory Values	Safety Set
Table 14.3.4	Vital Signs	Safety Set
Table 14.3.5	Shift Table of Physical Examination	Safety Set
Table 14.3.6	Electrocardiogram	Safety Set
Table 14.3.7	Study Drug Exposure and Compliance	Full Analysis Set

Table 14.3.8	Prior Medications	Full Analysis Set
Table 14.3.9.1	Concomitant Medications	Full Analysis Set
Table 14.3.9.2	Changes in Concomitant Medications	Full Analysis Set

14.2 LIST OF LISTINGS

Patient Data Listings

Listing 16.2.1.1	Patient Disposition
Listing 16.2.1.2	Discontinued Patients
Listing 16.2.2	Protocol Deviations
Listing 16.2.3	Analysis Datasets
Listing 16.2.4	Demographic Data
Listing 16.2.5	Study Drug Exposure and Compliance
Listing 16.2.6	Efficacy Response Data: ACR20/50/70 Response
Listing 16.2.7	Adverse Event Listing
Listing 16.2.8.1	Laboratory Measurements: Haematology
Listing 16.2.8.2	Laboratory Measurements: Biochemistry

Individual Patient Data Listings (Archive)

Listing 16.4.1	Final Status
Listing 16.4.2	Patient Visit Dates
Listing 16.4.3.1	Inclusion Criteria
Listing 16.4.3.2	Exclusion Criteria
Listing 16.4.4	Medical History
Listing 16.4.5.1	Raw Efficacy Data: Individual Components of the ACR20 Response
Listing 16.4.5.2	Raw Efficacy Data: ESR, DAS28-CRP, DAS28-ESR, SDAI Score, CDAI Score and FACIT-Fatigue Score
Listing 16.4.5.3	Raw Efficacy Data: Different Responses and Remissions
Listing 16.4.9	Vital Signs
Listing 16.4.10	Physical Examination
Listing 16.4.11	12-Lead Electrocardiogram
Listing 16.4.12.1	Prior Medications

Listing 16.4.12.2	Concomitant Medications
Listing 16.4.12.3	Changes to Medications
Listing 16.4.13	Pregnancy Test
Listing 16.4.14	Laboratory Samples Collection

15 SHELLS FOR TABLES, FIGURES AND LISTINGS

The intended layouts for tables, figures and listings are presented. However, it may be appropriate for the Orion programmer to change the layouts, upon review of the data available, for completeness and clarity.

QCd output will be produced as Rich Text Format (.rtf) files for convenient inclusion in the CSR.

Subject to this, the following will apply:

- Layout will be landscape, fixed width, font size 8.
- Each output will have the heading:
ABX464-301 (left); date ddMMMyyyy (right)
- Table headings will define the analysis set used for the summary/analysis.
- All outputs will have a footer specifying the SAS program path and filename (left); page x/y (right)
- Tables will have a footer specifying the source listing
- Figures will have a footer specifying the source table or listing
- Additional footnotes will be included where appropriate for clarification.
- Treatment group and patient number and will be included in all listings.

ABX464-301

ddMMMyyyy

Table 14.1.1 Screening Failures (All Enrolled Patients)

	Total Enrolled (N=xx)
Total number of enrolled patients	xx
Screened	xx (xx.x%)
Randomised	xx (xx.x%)
Screening failure	xx (xx.x%)
Baseline failure	Xx (xx.x%)
Primary Reason for screening failure	
Inclusion criterion not met	xx (xx.x%)
Exclusion criterion	xx (xx.x%)
Withdrawal by patient	xx (xx.x%)
Etc	

The denominator for each percentage is the number of enrolled patients.

Source: Listing 16.2.1.1 and 16.2.1.2
Path\Filename

Page x/y

ABX464-301

ddMMMyyyy

Table 14.1.2 Patient Disposition (All Randomised Patients)

	ABX-464 100mg (N=xx)	ABX-464 50mg (N=xx)	Placebo (N=xx)	Total (N=xx)
Full Analysis Set	xx (xx.x%)	xx (xx.x%)	xx (xx.x%)	xx (xx.x%)
Safety Set	xx (xx.x%)	xx (xx.x%)	xx (xx.x%)	xx (xx.x%)
Efficacy Set 1	xx (xx.x%)	xx (xx.x%)	xx (xx.x%)	xx (xx.x%)
Efficacy Set 2	xx (xx.x%)	xx (xx.x%)	xx (xx.x%)	xx (xx.x%)
Per Protocol Set	xx (xx.x%)	xx (xx.x%)	xx (xx.x%)	xx (xx.x%)

The denominator for each percentage is the number of randomized patients in the column.

Source: Listing 16.2.1.1 and 16.2.1.2
Path\Filename

Page x/y

ABX464-301

ddMMMyyyy

Table 14.1.3 Study Termination and Primary Reason for Withdrawal (All Randomised Patients)

	ABX-464 100mg (N=xx)	ABX-464 50mg (N=xx)	Placebo (N=xx)	Total (N=xx)
Randomised	xx	xx	xx	xx
Completed	xx (xx.x%)	xx (xx.x%)	xx (xx.x%)	xx (xx.x%)
Early withdrawal	xx (xx.x%)	xx (xx.x%)	xx (xx.x%)	xx (xx.x%)
Main reason for early withdrawal				
Investigator's decision	xx (xx.x%)	xx (xx.x%)	xx (xx.x%)	xx (xx.x%)
Adverse event	xx (xx.x%)	xx (xx.x%)	xx (xx.x%)	xx (xx.x%)
Major protocol violation	xx (xx.x%)	xx (xx.x%)	xx (xx.x%)	xx (xx.x%)
Patient's decision	xx (xx.x%)	xx (xx.x%)	xx (xx.x%)	xx (xx.x%)
Withdrawal of consent	xx (xx.x%)	xx (xx.x%)	xx (xx.x%)	xx (xx.x%)
Etc	xx (xx.x%)	xx (xx.x%)	xx (xx.x%)	xx (xx.x%)

The denominator for each percentage is the number of randomized patients in the column. Completed defined as performed follow-up visit.

Source: Listing 16.2.1.1 and 16.2.1.2
Path\Filename

Page x/y

ABX464-301

ddMMMyyyy

Table 14.1.4 Demographic and Baseline Characteristics (Full Analysis Set)

		ABX-464 100mg (N=xx)	ABX-464 50mg (N=xx)	Placebo (N=xx)	Total (N=xx)
Age (years)	N	xx	xx	xx	xx
	Mean	xx.xx	xx.xx	xx.xx	xx.xx
	SD	xx.xx	xx.xx	xx.xx	xx.xx
	Median	xx.xx	xx.xx	xx.xx	xx.xx
	Minimum	xx.x	xx.x	xx.x	xx.x
	Maximum	xx.x	xx.x	xx.x	xx.x
Sex	N	xx	xx	xx	xx
	Male	xx (xx.x%)	xx (xx.x%)	xx (xx.x%)	xx (xx.x%)
	Female	xx (xx.x%)	xx (xx.x%)	xx (xx.x%)	xx (xx.x%)
Height (cm)	N	xx	xx	xx	xx
	Mean	xx.xx	xx.xx	xx.xx	xx.xx
	SD	xx.xx	xx.xx	xx.xx	xx.xx
	Median	xx.xx	xx.xx	xx.xx	xx.xx
	Minimum	xx.x	xx.x	xx.x	xx.x
	Maximum	xx.x	xx.x	xx.x	xx.x
Weight (kg)	N	xx	xx	xx	xx
	Mean	xx.xx	xx.xx	xx.xx	xx.xx
	SD	xx.xx	xx.xx	xx.xx	xx.xx
	Median	xx.xx	xx.xx	xx.xx	xx.xx
	Minimum	xx.x	xx.x	xx.x	xx.x
	Maximum	xx.x	xx.x	xx.x	xx.x
BMI (kg/m ²)	N	xx	xx	xx	xx
	Mean	xx.xx	xx.xx	xx.xx	xx.xx

	ABX-464 100mg (N=xx)	ABX-464 50mg (N=xx)	Placebo (N=xx)	Total (N=xx)
SD	xx.xx	xx.xx	xx.xx	xx.xx
Median	xx.xx	xx.xx	xx.xx	xx.xx
Minimum	xx.x	xx.x	xx.x	xx.x
Maximum	xx.x	xx.x	xx.x	xx.x

The denominator for each percentage is the number of non-missing observations within the column
 Age was calculated using DOB and date of first treatment (Visit 1) and presented as age at last birthday.
 BMI is the patient's body weight in kilograms divided by the square of the patient's height in metres.

Source: Listing 16.2.4
 Path\Filename

Page x/y

ABX464-301

ddMMMyyyy

Table 14.1.5.1 Medical History (Full Analysis Set)

	ABX-464 100mg (N=xx)	ABX-464 50mg (N=xx)	Placebo (N=xx)	Total (N=xx)
Any medical/surgical history	xx (xx.x%)	xx (xx.x%)	xx (xx.x%)	xx (xx.x%)
SOC	xx (xx.x%)	xx (xx.x%)	xx (xx.x%)	xx (xx.x%)
PT	xx (xx.x%)	xx (xx.x%)	xx (xx.x%)	xx (xx.x%)
Etc	xx (xx.x%)	xx (xx.x%)	xx (xx.x%)	xx (xx.x%)
SOC	xx (xx.x%)	xx (xx.x%)	xx (xx.x%)	xx (xx.x%)
PT	xx (xx.x%)	xx (xx.x%)	xx (xx.x%)	xx (xx.x%)
Etc	xx (xx.x%)	xx (xx.x%)	xx (xx.x%)	xx (xx.x%)
Etc				

The denominator for each percentage is the number of patients within the column.
Medical history refers to conditions which stopped prior to or at the screening visit.

Source: Listing 16.4.4
Path\Filename

Page x/y

*This layout also applies to:
Table 14.1.5.2 Current Medical Conditions (Full Analysis Set) [Programmer's Note: Update footnote to medical conditions definition.]*

ABX464-301

ddMMMyyyy

Table 14.2.1.1 Analysis of ACR20 Response Rate (Efficacy Set 1)

		ABX-464 100mg (N=xx)	ABX-464 50mg (N=xx)	Placebo (N=xx)	p-value
ACR20 Response	N	xx	xx	xx	
	Yes	xx (xx.x%)	xx (xx.x%)	xx (xx.x%)	
	No	xx (xx.x%)	xx (xx.x%)	xx (xx.x%)	
Chi-squared test					x.xxxx

Response rate between treatments is compared using likelihood ratio chi-square test at a two-sided 10% significance level.

Source: Listing 16.2.6
Path\Filename

Page x/y

This layout also applies to:
Table 14.2.1.2 Analysis of ACR20 Response Rate (Efficacy Set 2)
Table 14.2.1.3 Analysis of ACR20 Response Rate (PP Set)

ABX464-301

ddMMMyyyy

Table 14.2.2.1 Summary of Categorical ACR20 Response at Week 12 (Efficacy Set 1)

		ABX-464 100mg (N=xx)	ABX-464 50mg (N=xx)	Placebo (N=xx)
Week 12	N	xx	xx	xx
	Rate	xx.x %	xx.x %	xx.x %
	Stratified 95% CI	xx.x % - xx.x %	xx.x % - xx.x %	xx.x % - xx.x %

Source: Listing 16.2.6
Path\Filename

Page x/y

This layout also applies to:
Table 14.2.2.2 Summary of Categorical ACR20 Response at Week 12 (Efficacy Set 2)

ABX464-301

ddMMMyyyy

Table 14.2.3.1 Analysis of the individual components of the ACR20 response (Efficacy Set 1)

		ABX-464 100mg (N=xx)	ABX-464 50mg (N=xx)	Placebo (N=xx)	p-value
CRP					
Baseline	N	xx (xx.x %)	xx (xx.x %)	xx (xx.x %)	
	Mean	xx.xx	xx.xx	xx.xx	
	Stratified 95% CI	xx.xx - xx.xx	xx.xx - xx.xx	xx.xx - xx.xx	
	SD	xx.xx	xx.xx	xx.xx	
	Minimum	xx.x	xx.x	xx.x	
	Maximum	xx.x	xx.x	xx.x	
	Median	xx.xx	xx.xx	xx.xx	
	Quartiles	xx.xx - xx.xx	xx.xx - xx.xx	xx.xx - xx.xx	
Week 2	N	xx (xx.x %)	xx (xx.x %)	xx (xx.x %)	
	Mean	xx.xx	xx.xx	xx.xx	
	Etc				
Change from baseline to Week 2	N	xx (xx.x %)	xx (xx.x %)	xx (xx.x %)	
	Mean	xx.xx	xx.xx	xx.xx	
	Etc				
Analysis of Covariance (change from baseline to Week 2)					x.xxxx
Week 4	N	xx (xx.x %)	xx (xx.x %)	xx (xx.x %)	
	Mean	xx.xx	xx.xx	xx.xx	
	Etc				
Etc					

Etc

Mixed model analysis of covariance is conducted for the changes of baseline for each parameter.

Source: Listing 16.4.5.1
Path\Filename

Page x/y

Programmer's Note: List of variables consists of CRP, TJC, SJC, Pain-VAS, PtGA, PrGA, HAQ-DI.

This layout also applies to:

Table 14.2.3.2 Analysis of the individual components of the ACR20 response (Efficacy Set 2)

ABX464-301

ddMMMyyyy

Table 14.2.4.1.1 Analysis of ESR (Efficacy Set 1)

		ABX-464 100mg (N=xx)	ABX-464 50mg (N=xx)	Placebo (N=xx)	p-value
Baseline	N	xx (xx.x %)	xx (xx.x %)	xx (xx.x %)	
	Mean	xx.xx	xx.xx	xx.xx	
	Stratified 95% CI	xx.xx - xx.xx	xx.xx - xx.xx	xx.xx - xx.xx	
	SD	xx.xx	xx.xx	xx.xx	
	Minimum	xx.x	xx.x	xx.x	
	Maximum	xx.x	xx.x	xx.x	
	Median	xx.xx	xx.xx	xx.xx	
	Quartiles	xx.xx - xx.xx	xx.xx - xx.xx	xx.xx - xx.xx	
Week 2	N	xx (xx.x %)	xx (xx.x %)	xx (xx.x %)	
	Mean	xx.xx	xx.xx	xx.xx	
	Etc				
Change from baseline to Week 2	N	xx (xx.x %)	xx (xx.x %)	xx (xx.x %)	
	Mean	xx.xx	xx.xx	xx.xx	
	Etc				
Analysis of Covariance (change from baseline to Week 2)					x.xxxx
Week 4	N	xx (xx.x %)	xx (xx.x %)	xx (xx.x %)	
	Mean	xx.xx	xx.xx	xx.xx	
	Etc				
Etc					

Mixed model analysis of covariance is conducted for the changes of baseline for each parameter.

Source: Listing 16.4.5.2
Path\Filename

Page x/y

This layout also applies to:

Table 14.2.4.1.2 Analysis of ESR (Efficacy Set 2)
Table 14.2.4.2.1 Analysis of DAS28-CRP (Efficacy Set 1)
Table 14.2.4.2.2 Analysis of DAS28-CRP (Efficacy Set 2)
Table 14.2.4.3.1 Analysis of DAS28-ESR (Efficacy Set 1)
Table 14.2.4.3.2 Analysis of DAS28-ESR (Efficacy Set 2)
Table 14.2.4.4.1 Analysis of SDAI Score (Efficacy Set 1)
Table 14.2.4.4.2 Analysis of SDAI Score (Efficacy Set 2)
Table 14.2.4.5.1 Analysis of CDAI Score (Efficacy Set 1)
Table 14.2.4.5.2 Analysis of CDAI Score (Efficacy Set 2)

ABX464-301

ddMMMyyyy

Table 14.2.4.6.1 Summary of FACIT-Fatigue Score (Efficacy Set 1)

		ABX-464 100mg (N=xx)	ABX-464 50mg (N=xx)	Placebo (N=xx)
Baseline	N	xx (xx.x %)	xx (xx.x %)	xx (xx.x %)
	Mean	xx.xx	xx.xx	xx.xx
	Stratified 95% CI	xx.xx - xx.xx	xx.xx - xx.xx	xx.xx - xx.xx
	SD	xx.xx	xx.xx	xx.xx
	Minimum	xx.x	xx.x	xx.x
	Maximum	xx.x	xx.x	xx.x
	Median	xx.xx	xx.xx	xx.xx
	Quartiles	xx.xx - xx.xx	xx.xx - xx.xx	xx.xx - xx.xx
Week 2	N	xx (xx.x %)	xx (xx.x %)	xx (xx.x %)
	Mean	xx.xx	xx.xx	xx.xx
	Etc			
Change from baseline to Week 2	N	xx (xx.x %)	xx (xx.x %)	xx (xx.x %)
	Mean	xx.xx	xx.xx	xx.xx
	Etc			
Week 4	N	xx (xx.x %)	xx (xx.x %)	xx (xx.x %)
	Mean	xx.xx	xx.xx	xx.xx
	Etc			
Etc				

Source: Listing 16.4.5.2
Path\Filename

Page x/y

This layout also applies to:
Table 14.2.4.6.2 Summary of FACIT-Fatigue Score (Efficacy Set 2)

ABX464-301

ddMMMyyyy

Table 14.2.5.1 Summary of Patients Achieving Different Responses and Remissions (Efficacy Set 1)

		ABX-464 100mg (N=xx)	ABX-464 50mg (N=xx)	Placebo (N=xx)
ARC20 Response				
Week 2	N	xx	xx	xx
	Rate	xx.x %	xx.x %	xx.x %
	Stratified 95% CI	xx.x % - xx.x %	xx.x % - xx.x %	xx.x % - xx.x %
Week 4	N	xx	xx	xx
	Rate	xx.x %	xx.x %	xx.x %
	Stratified 95% CI	xx.x % - xx.x %	xx.x % - xx.x %	xx.x % - xx.x %
Etc				
Etc				

Source: Listing 16.4.5.3
Path\Filename

Page x/y

Programmer's Note: List of variables consists of ACR20/50/70 response, Categorical DAS28-CRP response, LDA, DAS28-ESR remission, ACR/EULAR remission, SDAI remission, CDAI remission.

This layout also applies to:

Table 14.2.5.2 Summary of Patients Achieving Different Responses and Remissions (Efficacy Set 2)

ABX464-301

ddMMMyyyy

Table 14.3.1.1 Summary of Adverse Events (Safety Set)

	ABX-464 100mg (N=xx)		ABX-464 50mg (N=xx)		Placebo (N=xx)		Total (N=xx)	
	n	N (%)	n	N (%)	n	N (%)	n	N (%)
Any Adverse Event	xx	xx (xx.x%)	xx	xx (xx.x%)	xx	xx (xx.x%)	xx	xx (xx.x%)
Any Treatment-Emergent Adverse Event	xx	xx (xx.x%)	xx	xx (xx.x%)	xx	xx (xx.x%)	xx	xx (xx.x%)
Any Serious Adverse Event	xx	xx (xx.x%)	xx	xx (xx.x%)	xx	xx (xx.x%)	xx	xx (xx.x%)
Adverse Event leading to death	xx	xx (xx.x%)	xx	xx (xx.x%)	xx	xx (xx.x%)	xx	xx (xx.x%)
Any grade 3 or higher Adverse Event	xx	xx (xx.x%)	xx	xx (xx.x%)	xx	xx (xx.x%)	xx	xx (xx.x%)

The table presents number of events (n) and number and percentage of patients (N(%)).
The denominator for each percentage is the number of patients within the column.

Source: Listing 16.2.7
Path\Filename

Page x/y

ABX464-301

ddMMMyyyy

Table 14.3.1.2.1 Analysis of Treatment-Emergent Adverse Events (Safety Set)

		ABX-464 100mg (N=xx)	ABX-464 50mg (N=xx)	Placebo (N=xx)	p-value
Any Treatment-Emergent Adverse Event	N	xx	xx	xx	
	Yes	xx (xx.x%)	xx (xx.x%)	xx (xx.x%)	
	No	xx (xx.x%)	xx (xx.x%)	xx (xx.x%)	
Chi-squared test					x.xxxx

The denominator for each percentage is the number of patients within the column
TEAE rate between treatments is compared using likelihood ratio chi-square test at a two-sided 10% significance level.

Source: Listing 16.2.7
Path\Filename

Page x/y

ABX464-301

ddMMMyyyy

Table 14.3.1.2.2 Treatment-Emergent Adverse Events, by SOC and PT: Period 1 (Safety Set)

	ABX-464 100mg (N=xx)			ABX-464 100mg (N=xx)			Placebo (N=xx)			Total (N=xx)		
	n	N (%)	duration (days)	n	N (%)	duration (days)	n	N (%)	duration (days)	n	N (%)	duration (days)
Any Treatment-Emergent Adverse Event	xx	xx (xx.x%)		xx	xx (xx.x%)		xx	xx (xx.x%)		xx	xx (xx.x%)	
SOC	xx	xx (xx.x%)	xx.xx	xx	xx (xx.x%)	xx.xx	xx	xx (xx.x%)	xx.xx	xx	xx (xx.x%)	xx.xx
PT	xx	xx (xx.x%)	xx.xx	xx	xx (xx.x%)	xx.xx	xx	xx (xx.x%)	xx.xx	xx	xx (xx.x%)	xx.xx
PT	xx	xx (xx.x%)	xx.xx	xx	xx (xx.x%)	xx.xx	xx	xx (xx.x%)	xx.xx	xx	xx (xx.x%)	xx.xx
SOC Etc	xx	xx (xx.x%)	xx.xx	xx	xx (xx.x%)	xx.xx	xx	xx (xx.x%)	xx.xx	xx	xx (xx.x%)	xx.xx
Etc												

The table presents number of events (n) and number and percentage of patients (N(%)).
The denominator for each percentage is the number of patients within the column.
Duration (days) represents median duration of AEs (from baseline to occurrence).

Source: Listing 16.2.7
Path\Filename

Page x/y

This layout also applies to:

Table 14.3.1.2.3 Treatment-Emergent Adverse Events, by SOC and PT: Period 2 (Safety Set)

Table 14.3.1.3.1 Serious Treatment-Emergent Adverse Events, by SOC and PT: Period 1 (Safety Set)

Table 14.3.1.3.2 Serious Treatment-Emergent Adverse Events, by SOC and PT: Period 2 (Safety Set)

Table 14.3.1.4.1 Treatment-Emergent Adverse Events Leading to Study Drug Discontinuation, by SOC and PT: Period 1 (Safety Set)

Table 14.3.1.4.2 Treatment-Emergent Adverse Events Leading to Study Drug Discontinuation, by SOC and PT: Period 2 (Safety Set)

Table 14.3.1.5.1 Treatment-Emergent Adverse Events of Grade 3 or 4 by SOC and PT: Period 1 (Safety Set)

Table 14.3.1.5.2 Treatment-Emergent Adverse Events of Grade 3 or 4 by SOC and PT: Period 2 (Safety Set)

ABX464-301

ddMMyyyy

Table 14.3.2.1 Listing of Deaths (Safety Set)

Treatment	Patient number	Date of death	Cause of death
xxxxxx	xxx-xxxx	ddMMyyyy	xxxxxxxxxxxxxxxxxxxx
xxxxxx	xxx-xxxx	ddMMyyyy	xxxxxxxxxxxxxxxxxxxx
Etc			

Path\filename

Page x/y

ABX464-301

ddMMMyyyy

Table 14.3.2.2 Listing of Serious Adverse Events

Treatment	Centre/ Patient number	Adverse Event PT SOC	Onset date	Resolution date / ongoing	Outcome	Relationship to study drug	Action taken with study drug	Other action taken
xxxxx	xxx-xxxx	xxxxxxxxxx xxxxxxxx xxxx	ddMMMyyyy	ddMMMyyyy / ongoing	Resolved/ Resolved without sequelae/ Etc	Yes/No	None/ Temporary discontinuation/ Etc	Concomitant medication (CM no.)/ Procedure (PR no.)
		xxxxxxxxxx xxxxxxxx xxxx	ddMMMyyyy	ddMMMyyyy / ongoing	Resolved/ Resolved without sequelae/ Etc	Yes/No	None/ Temporary discontinuation/ Etc	Concomitant medication (CM no.)/ Procedure (PR no.)
		Etc						
Etc								

Path\Filename

Page x/y

